9.5.3 E-DBTP Analyses of Exploratory Efficacy Endpoints

The dichotomous efficacy endpoints for assessing qualifying triptan-treated attacks only in E-DBTP will be analyzed using logistic regression model with missing data imputed as non-responders (NRI) **up to End of Study Date**. Odds ratios of treatment group and placebo with associated 95% CIs and p-values will be reported. The efficacy endpoint for Migraine Interictal Burden Scale at month 4 will be analyzed using the linear mixed effects model that includes treatment group, baseline values, scheduled visit, and the interaction of treatment and scheduled visit without any imputation for missing data.

The following exploratory endpoints of the E-DBTP for the first qualifying triptan-treated attack will be analyzed by medication overuse status at month 3 (yes vs. no):

- Achievement of pain freedom at 2 hours post-triptan dose for the first attack at month 4
- Achievement of pain relief at 2 hours post-triptan dose for the first attack at month 4
- Achievement of relief from the most bothersome symptom at 30, 60, and 120 minutes post-triptan dose for the first attack at month 4
- Achievement of 24-hour sustained pain freedom post-triptan dose for the first attack at month 4
- Migraine recurrence within 24 hours post-triptan dose for the first attack at month 4
- Use of migraine rescue medication within 24 hours post-triptan dose for the first attack at month 4

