4.1 Planned Covariates

For efficacy endpoints of the M-DBTP, all model-adjusted analyses of efficacy endpoints will include the corresponding baseline value for the endpoint being analyzed. The baseline value is calculated based on data collected during the 4-week baseline period or on day 1 prior to the first dose.

For pain freedom and pain relief related efficacy endpoints of the E-DBTP (month 4), the following covariates may be considered:

• Medication overuse status at month 3 (yes vs no)

- Time to triptan intake since reaching moderate/severe pain of the first qualifying attack at month 4 (< 1 hour vs ≥ 1 hour)
- Pain intensity prior to triptan intake is severe (yes [NRS ≥ 7] vs no) of the first qualifying attack at month 4

For most bothersome symptom related endpoints of the E-DBTP, the following symptom types may be included in the model:

- Nausea/Vomiting (yes vs no)
- Photophobia/phonophobia (yes vs no)

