4.2 Subgroups

The primary and secondary endpoints of the M-DBTP will be analyzed in the following subgroups:

- Number of prior treatment failures (1, 2, and 3 or more treatment failures)
- Medication overuse status at baseline (yes vs. no)

Selected exploratory endpoints of the E-DBTP for the first qualifying triptan-treated attack may be analyzed by medication overuse status at month 3 (yes vs. no) (see Section 9.5.3).

The subgroups will be re-examined for appropriateness and may be re-categorized (due to small sample size, for example, if there are < 10% of subjects within a subgroup) before unblinding.

5. Definitions

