5.1 Definition of Terms Included in Study Endpoints

5.1.1 Efficacy Endpoints Based on Daily Diary Data Collection During M-DBTP

During the 4-week baseline period and the 12-week M-DBTP, headache start and stop date/time, pain feature/symptoms, acute headache medication and aura related information will be reported on a daily basis via optional any-time diar(ies) (available 24 hours) and mandatory evening diary (only available once daily from 17:00 to 23:59).

Acute Headache Medication (AHM)

Acute headache medications collected in the eDiary are classified separately as follows:

	Medication Group A
Acute headache medication (AHM)	Ergotamine-Based Migraine Medications
	Triptan-Based Migraine Medications
	Gepant-Based Migraine Medications
	Ditan-Based Migraine Medications

Non-Opioid Acute Headache Medications
Non-Opioid Butalbital Containing Medications
Opioid-Containing Acute Headache Medications
Opioid-Containing Butalbital Containing Medications

	Medication Group B
	Ergots
	Triptans
	Gepants
Acute headache medication	Ditans
(AHM)	Opiate or opioid-containing medication
	Opioid Combination-analgesic
	Non-opioid Combination-analgesic
	Simple analgesics/NSAIDs

Acute Migraine-specific Medication (AMSM)

A subset of acute headache medication consisting of triptan-based migraine medications and ergotamine-based migraine medications

Medication Overuse (MO)

Monthly acute headache medication days meeting at least one of the following criteria based on medication category B:

- \geq 10 days of triptans
- \geq 10 days of ergotamines
- ≥ 10 days of opiates or opioid-containing medications or opioid combination-analgesics
- \geq 10 days of non-opioid combination-analgesics
- ≥ 15 days of simple analgesics/NSAIDs if no other acute headache medications were used
- ≥ 10 days of a combination of triptans, ergotamines, opiates or opioid-containing meds or opioid combination-analgesic, non-opioid combination-analgesic medications or simple analgesics/NSAIDs whilst not satisfying medication overuse criteria in any of the individual medication categories alone

Number of Diary Days in a Monthly Interval	Monthly Days with Medication Use
• ≥ 14 days	Prorate to 28-day equivalent without rounding Number of observed days with medication use*28/number of (diary days or medication days) within each monthly interval
• < 14 days	Set to missing

Qualified Headache

A qualified headache is defined as

- A headache of duration \geq 30 minutes, or

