9.5.1 Analyses of Primary and Secondary Efficacy Endpoints

For the primary and secondary endpoints will be tested using a linear mixed model based on observed monthly data with appropriate contrasts for pairwise treatment comparisons.

The model will include treatment, scheduled visit, treatment by visit interaction, and baseline value as covariates. If applicable, the first-order autoregressive covariance structure is assumed. Least squares means (LSMs) for each treatment group, standard errors, associated 95% CIs, difference of LSMs compared to placebo group, associated 95% CIs and nominal two-sided p-values will be tabulated by visit and treatment, as well as for the mean monthly values over months 1, 2, and 3 of the DBTP. No sensitivity analyses will be performed for the primary and secondary endpoints.

Subgroup analysis described below will be performed for the primary and secondary endpoints:

- 1. Treatment failure of prior migraine prophylactic medications (1, 2, and 3 or more treatment failures)
- 2. Medication overuse at baseline (yes vs. no)

The purpose of the subgroup analyses is to explore if the treatment effect varies across subgroups of interest. Subgroup analyses are performed for primary and secondary efficacy endpoints using the same method as primary analysis method but performed within each interested subgroup.

The heterogeneity of the treatment effect across the subgroups will be evaluated by examining the treatment-by-subgroup interaction at primary time point and an interaction p-value will be presented. The primary analysis model with the addition of treatment-by-subgroup interaction will be used.

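### Six exploratory month-4 endpoints are compared within strata of month-3 medication overuse, which treatment can change; baseline overuse is already derived and should be used for the treatment comparison

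*SAP*

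**What the plan says.** SAP 9.5.3 lists six month-4 endpoints for the first qualifying triptan-treated attack and says they "will be analyzed by medication overuse status at month 3 (yes vs. no". Because relief from the most bothersome symptom is assessed at three times, the six items amount to eight comparisons, or 16 odds ratios over two strata. Earlier in the same section, the general output for the dichotomous month-4 endpoints is given: "Odds ratios of treatment group and placebo with associated 95% CIs and p-values will be reported". What is reported within strata is not stated.

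SAP 4.2 describes the same split more loosely: selected endpoints "may be analyzed by medication overuse status at month 3 (yes vs. no) (see Section 9.5.3". SAP 4.1 lists "Medication overuse status at month 3 (yes vs no" as a covariate that may be considered for the pain freedom and pain relief endpoints.

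SAP 5.1.1 defines overuse by thresholds of 10 or 15 days, depending on drug class: "Monthly acute headache medication days meeting at least one of the following criteria based on medication category B". Days are prorated to a 28-day month ("Number of observed days with medication use*28/number of" of diary or medication days), and the count is set to missing below 14 diary days. In SAP Table 5-1, month 3 runs from the week 8 dose date to the day before the week 12 dose.

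For the primary and secondary endpoints the SAP uses the pre-treatment version instead: "Medication overuse status at baseline (yes vs. no" in 4.2 and "Medication overuse at baseline (yes vs. no" in 9.5.1.

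**The concern.** A subgroup comparison keeps the protection of randomisation when treatment cannot affect subgroup membership. Month-3 overuse does not meet that condition. It is measured after the day 1, week 4 and week 8 doses, and its components are acute-medication days, which the protocol expects erenumab to reduce. If the drug moves some subjects out of overuse, the erenumab subjects still overusing are a different selection from the placebo overusers, and the erenumab non-overusers now include subjects who would otherwise have been overusing. Any cause shared by overuse and triptan response then shows up as a treatment difference within a stratum.

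A reader could take such an odds ratio as an effect on triptan response in current overusers or non-overusers when part of it reflects who left overuse on drug. Depending on how overuse relates to response, this could hide a benefit or create one. Assessing response to acute triptan treatment is a stated purpose of the month-4 phase, so these tables are likely to be read. They lie outside the sequential testing procedure, so the stake is interpretation and not type I error control.

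**Working it through.** **Plan figures.** The documents give no figure for the month-4 endpoints, for overuse rates or for the split. The only planning figure needed is the number per arm: 288 × 0.9 = 259.2. As a check, the stated 96% primary power reproduces with it: 16.7 / (50 × √(2/259.2)) = 3.80; 3.80 − 1.96 = 1.84; power 96.7%. For month 4, 259 is an upper bound, because a week 12 dose (SAP 6.3), a qualifying attack with 2-hour data (SAP 2.1) and at least 14 diary days in month 3 are also required.

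**Illustration with no treatment effect on the outcome.** All inputs here are assumptions.
- A latent factor U ~ N(0,1) represents a shared cause.
- Month-3 overuse occurs when a liability with correlation ρ to U exceeds an arm-specific threshold. Placebo overuse is 40%; erenumab overuse is 35%, 30% or 20%.
- Outcome logit = −0.9 − cU for a favourable outcome or −0.9 + cU for an unfavourable one, with c = 0.5 or 1.0. The overall rate is 30% to 32% in both arms.
- ρ = ±0.3, ±0.6, ±0.8. Stratum probabilities are found by numerical integration.

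**One cell in full** (favourable outcome, ρ = 0.8, c = 1.0, overuse 40% against 20%):
- Overuse: 0.1359 on erenumab, 0.1812 on placebo. OR = (0.1359/0.8641) / (0.1812/0.8188) = 0.1572/0.2213 = 0.71.
- No overuse: 0.3677 and 0.4147. OR = 0.5815/0.7086 = 0.82.
- Overall: 0.321 in both arms, OR 1.00.

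**Whole grid at 40% placebo overuse:**

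| Outcome and link | Overuse OR | No-overuse OR |
|---|---|---|
| Favourable, overuse marks poorer response (ρ > 0) | 0.71 to 0.99 | 0.82 to 0.99 |
| Favourable, overuse marks better response (ρ < 0) | 1.01 to 1.37 | 1.01 to 1.26 |

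Unfavourable outcomes mirror these. The ratio of the two stratum ORs runs from 0.87 to 1.08. Under this model, ρ = 0 or equal overuse in both arms gives 1.00 in both strata.

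**Other placebo rates, same falls:**

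| Placebo overuse | Overuse OR | No-overuse OR |
|---|---|---|
| 25% | 0.54 to 1.79 (extremes need a fall to 5%) | 0.82 to 1.28 |
| 55% | 0.77 to 1.27 | 0.81 to 1.28 |

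**Against sampling error.** CI factor = exp(1.96 × SE of the log OR), where SE² is the sum over arms of 1/(n·p·(1 − p)), with n the stratum size in that arm. For the overuse stratum of the cell above, n = 259 × 0.2 = 51.8 and 259 × 0.4 = 103.6. SE = √(1/6.08 + 1/15.37) = 0.479, so the factor is exp(0.939) = 2.56. Over the grid at 40%:

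| Per arm | Overuse | No overuse |
|---|---|---|
| 259 | 1.8 to 2.6 | 1.5 to 1.7 |
| 150 (assumed) | 2.1 to 3.4 | 1.8 to 2.0 |

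At 259 per arm the largest |log OR| is 0.48 of the CI half-width at 40% overuse, and 0.59 over the 25% to 55% range.

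**Baseline against month 3.** A separate simulation of 4,000,000 subjects assumed 40% overuse at baseline, 35% at month 3 on placebo and 30% down to 15% on erenumab, liability correlation 0.7, slopes 0.5 and 1.0, and no true effect. Splitting by month-3 overuse gave ORs of 0.72 to 0.98, with a per-stratum false-positive rate of 5.1% to 12.2% at 259 per arm. Splitting the same subjects by baseline overuse gave 0.99 to 1.01 throughout.

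**The case against.** The strongest reply is that the month-3 split asks a different question. Month 3 is the last daily-diary month before the episode diary, so it measures overuse close to the attack, whereas the baseline interval lies about 12 weeks earlier. That is a good reason to keep the month-3 split as a description. It does not make the treatment contrast within it a randomised one.

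The numbers also rest on one mechanism. If overusers instead leave overuse independently of the latent factor (40% to 20%), the overuse-stratum OR is exactly 1.00 and only the no-overuse OR moves, to 0.78 to 0.95 for ρ > 0. Equal overuse rates guarantee 1.00 only under the threshold model. The ratio of stratum ORs depends on the assumed rate: at 25% placebo overuse it is 0.65 to 1.39. All this is correct. It shows that size and pattern cannot be known in advance, but the alternative mechanism still biases one stratum.

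Three further points stand as limits:
- SAP 9.5.3 does not say that p-values will be given within strata, so a descriptive reading is possible, though the text does not require it.
- Table 9-3 fits treatment group alone for the pain freedom and pain relief models it covers, so the covariate entry in SAP 4.1 is leftover wording more than a planned adjustment.
- A baseline split does not restore full randomisation, because selection on the week 12 dose and on having a qualifying attack remains. That selection also affects the unsplit comparison and is no reason to add a second, avoidable source.

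**Conclusion.** The concern holds, at minor severity. That the stratifier is measured on treatment, that the protocol expects treatment to affect its components, and that a baseline version is already prespecified all follow from the documents. The size and direction of any bias do not: they depend on the overuse rates in each arm, the link between overuse and triptan response, and how subjects leave overuse. The ranges above are illustrations. Under those assumptions the shift is smaller than the sampling error of a stratum estimate, but unlike sampling error it would not shrink with more subjects. Nothing in the primary, secondary or overall month-4 results changes.

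**What to change.** In SAP 9.5.3, replace month 3 by baseline as the overuse stratifier for the treatment comparison in the six listed endpoints, and change the matching sentence in SAP 4.2. In the same edit, reconcile the optional wording in 4.2 with the firm wording in 9.5.3, and state what is reported within strata. If the month-3 split is wanted, keep it as a descriptive table by arm, labelled as not supporting a causal reading and without p-values, and say how subjects with fewer than 14 diary days in month 3 are shown.

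In SAP 4.1, remove month-3 overuse from the optional covariates so that the text agrees with Table 9-3. The other two covariates listed there for these endpoints describe the month-4 attack itself and also arise after randomisation, so they should be reviewed at the same time.

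The cost is wording only. Baseline overuse is already derived and should rarely be missing: inclusion criterion 111 requires 80% diary compliance, and 0.8 × 28 = 22.4 days is well above the 14-day minimum. What is lost is an inferential split by current overuse.

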•	To evaluate the treatment benefit of erenumab on duration of migraine pain of at least moderate intensity in months with at least 1 migraine attack (migraine attacks as defined in Section 11.1)	•	Change from baseline in mean monthly average duration of at least moderate pain intensity per migraine attack over months 1, 2, and 3	
•	To evaluate the treatment benefit of erenumab on peak migraine pain intensity in months with at least 1 migraine attack (migraine attacks as defined in Section 11.1)	•	Change from baseline in mean monthly average peak migraine pain intensity as assessed by the 11-point NRS over months 1, 2, and 3	
Ex	ploratory Double-blind Treatment Phase	(mor	nth 4)	
•	To evaluate the treatment benefit of erenumab on interictal burden of migraine	•	Change from baseline in Migraine Interictal Burden Scale (MIBS-4) total score at month 4	
For the first qualifying oral triptan-treated attack (defined in Section 11.1) with complete data at 2-hour assessment:				
•	To evaluate the treatment benefit of erenumab on achieving and	•	Achievement of pain freedom at 2 hours post-triptan dose for the first attack at month 4	
	sustaining pain freedom following treatment with an oral triptan		Achievement of 24-hour sustained pain freedom post-triptan dose for the first attack at month 4	
		•	Achievement of pain freedom at 30 and 60 minutes post-triptan dose for the first attack at month 4	
•	To evaluate the treatment benefit of erenumab on achieving pain relief following treatment with an oral triptan	•	Achievement of pain relief (defined in Section 11.1) at 30, 60, and 120 minutes post-triptan dose for the first attack at month 4	

•	To evaluate the treatment benefit of erenumab on achieving freedom from the most bothersome symptom following treatment with an oral triptan	•	Achievement of freedom from the most bothersome symptom at 30, 60, and 120 minutes post-triptan dose for the first attack at month 4
•	To evaluate the treatment benefit of erenumab on achieving relief from the most bothersome symptom following treatment with an oral triptan	•	Achievement of relief from the most bothersome symptom at 30, 60, and 120 minutes post-triptan dose for the first attack at month 4
•	To evaluate the treatment benefit of erenumab on migraine recurrence following treatment with an oral triptan	•	Migraine recurrence (defined in Section 11.1) during 24 hours post-triptan dose for the first attack at month 4

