Migraine recurrence	return of any headache of at least moderate pain intensity in patients who were pain-free at 2 hours post-dose
MMD	monthly migraine days
MSSS	Migraine Symptom Severity Score
NCT	National Clinical Trials
NRS	Numeric Rating Scale
pain relief	reduction from moderate/severe pain to mild/no pain
PCS	Pain Catastrophizing Scale
PFS	prefilled syringes
PGI-S	Patient Global Impression of Severity
PHQ-9	Patient Health Questionnaire
Q4W	every 4 weeks
QM	once monthly
Qualifying oral triptan-treated attacks (run-in period/month 4)	migraine attacks of at least moderate peak pain intensity that are treated with an oral triptan within 2 hours of pain reaching at least moderate severity
Qualifying oral triptan-treated attacks (baseline/ month 1, 2, and 3)	migraine attacks that are treated with an oral triptan
Randomization	defined as the day a subject has met all run-in and baseline period eligibility criteria and is enrolled and randomized into the study (subjects are enrolled same day)
SAP	statistical analysis plan
SC	subcutaneous(ly)

Abbreviation or Term	Definition/Explanation
Source d ata	information from an original record or certified copy of the original record containing patient information for use in clinical research. The information may include, but is not limited to, clinical findings, observations, or other activities in a clinical trial necessary for the reconstruction and evaluation of the trial. Source data are contained in source documents (original records or certified copies). (ICH Guideline [E6]). Examples of source data include Subject identification, Randomization identification, and Stratification Value.
Study d ay 1	defined as the first day that protocol-specified investigational product(s)/protocol-required therapies is/are administered to the subject
Total migraine freedom days	Days where there is an absence of headache and aura, photophobia, phonophobia, and nausea/vomiting
US	United States

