5.1.2 Efficacy Endpoints Based on Episodic Diary Data Collection During E-DBTP

During the 2-week run-in period and the 1-month E-DBTP at month 4, subjects experiencing a qualified triptan-treated migraine attack will report medication usage, pain intensity, the most bothersome symptom and corresponding severity using the episodic diary. A qualifying headache for reporting is a headache reaching at least moderate pain intensity with initial triptan intake within 2 hours and also satisfying migraine headache criteria (ie, a qualified triptan-treated migraine attack). The initial triptan intake time (ie, time point 0) will trigger a 48-hour assessment window, during which the headache pain intensity, severity of the most bothersome symptom at 30, 60 and 120 minutes, 24 hours and 48 hours post triptan will be collected. Another 48-hour assessment window will be triggered if there is a new qualified triptan-treated migraine attack starts after the previous assessment window.

Headache Pain Intensity (NRS) in E-DBTP

Worst or peak pain intensity collected on a headache ranges from 0 to 10 with a higher score indicating more severe pain.

NRS Pain intensity is collected when a qualified headache reaching at least moderate pain intensity with triptan intake within 2 hours and for the following timed assessments at 30 minutes, 1-hour, 2-hour, 24-hour and 48-hour diaries.

Migraine Rescue Medication

Migraine rescue medication for each qualifying triptan-treated attack is defined as any additional acute headache medication(s) taken during the 48-hour assessment window.

Migraine Recurrence Within 24 Hours Post-triptan

Pain intensity NRS = 0 at any of the 30-minute, 60-minute, and 2-hour timed assessments and pain intensity NRS \geq 4 at 24-hour timed assessment

Pain Relief at timed assessment post-triptan dose

Pain intensity NRS < 4 at the specific timed assessment (eg, 30 minutes, 60 minutes, or 2 hours post-triptan dose).

Pain freedom at timed assessment post-triptan dose

Pain intensity NRS = 0 at the specific timed assessment (eg, 30 minutes, 60 minutes or 2 hours post-triptan dose).

Achievement of 24-hour sustained pain freedom post-triptan dose

Pain intensity NRS = 0 at both 2-hour and 24-hour timed assessment without rescue medication taken post-triptan dose.

Most Bothersome Symptom

The most bothersome symptom can be selected among nausea, vomiting, sensitivity to light, or sensitivity to sound.

Severity of Most Bothersome Symptom (4-level)

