6.3 E-DBTP Efficacy Analysis Set

The E-DBTP efficacy analysis set consists of a subset of subjects from full analysis set who receive week 12 dose. Subjects will be analyzed according to their randomized treatment, regardless of treatment received. Analysis of exploratory efficacy endpoints during E-DBTP will utilize this efficacy analysis set.

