Change from baseline in social function domain as measured by MFIQ at assessment time points Change from baseline in emotional function domain score as measured by MFIQ at assessment time points

Change from baseline in overall impact on usual activities global item score as measured by MFIQ at assessment time points

Change from baseline in mean monthly average duration of at least moderate pain intensity per migraine attack in months with at least 1 migraine attack

Change from baseline in mean monthly peak migraine pain intensity as assessed by the 11-point Numeric Rating Scale (NRS) in months with at least 1 migraine attack

^b The same analyses methods will be applied to the endpoints: Change in Patient Global Impression of Severity (PGI-S) total score at month 3

^c The same analyses methods will be applied to the endpoints: Change from baseline in the most troublesome symptom (MTS) at month 3

 ^d The same analyses methods will be applied to the endpoints: Achievement of pain freedom at 30 and 60 minutes post-triptan dose for the first attack at month 4 Achievement of pain relief at 2 hours post-triptan dose for the first attack at month 4 Achievement of freedom from the most bothersome symptom at 30, 60, and 120 minutes post-triptan dose for the first attack at month 4 Achievement of relief from the most bothersome symptom at 30, 60, and 120 minutes post-triptan dose for the first attack at month 4 Achievement of 24-hour sustained pain freedom post-triptan dose for the first attack at month 4 Migraine recurrence during 24 hours post-triptan dose for the first attack at month 4

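### Month-4 migraine recurrence has no pain-free denominator in the SAP, so triptan failures are coded as no recurrence and the odds ratio mixes pain freedom with recurrence

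*SAP*

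**What the plan says.** Protocol 11.1 defines migraine recurrence as "return of any headache of at least moderate pain intensity in patients who were pain-free at 2 hours post-dose". The at-risk group is part of the definition.

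SAP 5.1.2 replaces this with a two-part event: "Pain intensity NRS = 0 at any of the 30-minute, 60-minute, and 2-hour timed assessments", together with NRS ≥ 4 at the 24-hour assessment.

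SAP Table 9-3, footnote d, lists "Migraine recurrence during 24 hours post-triptan dose for the first attack at month 4" among the endpoints that share the method for 2-hour pain freedom. That method is a logistic model with treatment as the only term and with missing outcomes imputed as non-responders. SAP 9.5.3 asks for odds ratios with 95% CIs and p-values, and lists "Migraine recurrence within 24 hours post-triptan dose for the first attack at month 4" again for analysis by medication overuse at month 3.

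On who is analysed, SAP 6.3 states: "The E-DBTP efficacy analysis set consists of a subset of subjects from full analysis set who receive week 12 dose". It adds: "Analysis of exploratory efficacy endpoints during E-DBTP will utilize this efficacy analysis set". The endpoint headings narrow this. Protocol Section 3 reads "For the first qualifying oral triptan-treated attack (defined in Section 11.1) with complete data at 2-hour assessment", SAP 2.1 carries a matching heading, and SAP 9.5.3 confines the model to qualifying triptan-treated attacks.

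No section of the SAP limits recurrence to subjects who became pain-free. SAP Section 10 declares one departure from the protocol, the change of analysis sets, and does not mention the recurrence definition.

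**The concern.** A headache can recur only after it has gone. Under the SAP definition, a subject whose triptan never produced pain freedom has complete data, fails the first part of the event, and takes the favourable code. That category then mixes treatment failures with subjects who became and stayed pain-free.

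The stated objective is erenumab's effect on recurrence after an oral triptan. Month 4 exists because erenumab may improve the acute response to triptans. If it does, more erenumab subjects become able to have the event at all, and the odds ratio moves against erenumab even when recurrence among pain-free subjects is the same in both arms. The overuse-stratified analysis has the same fault.

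**Working it through.** **Plan's own figure.** There is none to reproduce: neither document gives a rate, effect size or power for recurrence, or an expected number of month-4 attacks. All rates below are assumptions.

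**Step 1: how each subject is coded** (first qualifying triptan-treated attack, complete 2-hour data)

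| Course of the attack | Protocol 11.1 | SAP 5.1.2 with footnote d |
|---|---|---|
| Never pain-free by 2 h | not at risk | no recurrence |
| Pain-free at 2 h, no return of moderate pain | at risk, no recurrence | no recurrence |
| Pain-free at 2 h, NRS ≥ 4 at 24 h | recurrence | recurrence |
| Pain-free at 30 or 60 min but not at 2 h, NRS ≥ 4 at 24 h | not at risk | recurrence |

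The first row drives this point. The last row shows that the SAP numerator also departs from the 2-hour condition.

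**Step 2: formula.** Let p be the proportion pain-free and r the recurrence among them, with subscripts P (placebo) and E (erenumab).
- Analysed rate = p × r
- Reported OR = [p_E r_E / (1 − p_E r_E)] / [p_P r_P / (1 − p_P r_P)]
- At-risk OR = [r_E / (1 − r_E)] / [r_P / (1 − r_P)]

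**Step 3: equal recurrence among pain-free subjects, r = 25% in both arms (at-risk OR 1.00), p_P = 20%**
- p_E = 20%: 5.0% vs 5.0%, OR 1.00 (no distortion)
- p_E = 25%: 5.0% vs 6.25%, OR = (0.0625/0.9375)/(0.05/0.95) = 1.27
- p_E = 30%: 5.0% vs 7.5%, OR = (0.075/0.925)/(0.05/0.95) = 1.54
- p_E = 40%: 5.0% vs 10.0%, OR = (0.10/0.90)/(0.05/0.95) = 2.11

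Across pain-free rates of 20 vs 30%, 30 vs 40%, 30 vs 45% and 40 vs 50%, with r between 20% and 40% and equal in the two arms, the reported OR runs from 1.28 to 1.61.

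**Step 4: when the direction reverses.** The reported OR exceeds 1 only if r_E / r_P is greater than p_P / p_E. At 20 vs 30% pain-free the break-even ratio is 0.20/0.30 = 0.67, so recurrence among pain-free subjects must fall from 25% to 16.7% before the reported OR reaches 1.
- Fall from 25% to 20% (at-risk OR 0.75): 5.0% vs 6.0%, reported OR 1.21, the wrong direction.
- At 30 vs 40% pain-free with recurrence falling from 30% to 18% (at-risk OR 0.51): 9.0% vs 7.2%, reported OR 0.78, the right direction but diluted.

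**Step 5: subjects with no qualifying attack.** The SAP does not say whether they are excluded or imputed. If excluded, the figures above stand. If coded as no recurrence, the rate becomes P(attack) × p × r. Assuming 85% of placebo and 70% of erenumab subjects have such an attack, with 20 vs 30% pain-free and r = 25%: 0.85 × 5.0% = 4.25% vs 0.70 × 7.5% = 5.25%, OR 1.25 instead of 1.54. At 20 vs 25% pain-free the OR is 1.03 instead of 1.27. Fewer attacks on erenumab would partly offset the bias.

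**The case against.** **The protocol supplies the denominator.** The SAP says it details the protocol's analyses, Protocol 11.1 names the at-risk group, and the NRS = 0 clause could be read as putting that condition into effect. This does not remove the fault. The clause enters the event and not the denominator, and it also accepts pain freedom at 30 or 60 minutes. Where the SAP wants a restricted analysis it says so, as for the most troublesome symptom in SAP 5.1.3. The literal reading keeps triptan failures in.

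**A joint event is a legitimate endpoint.** It can be estimated, but it does not answer the recurrence objective because it rises with triptan success.

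**The consequence is small.** This stands. Recurrence is one of many exploratory month-4 endpoints outside the tested sequence. Pain freedom from the same attack is also reported, so a careful reader could see why the recurrence odds ratio had moved.

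**Stronger readings that the documents do not support**
- That every subject given the week 12 dose is in the denominator. SAP 6.3 names that set, but the endpoint headings and SAP 9.5.3 limit the analysis to qualifying triptan-treated attacks, and the headings require complete 2-hour data.
- That erenumab will inevitably appear to cause recurrence. Step 4 shows this depends on how far recurrence among pain-free subjects falls.
- That a chance of a nominally significant wrong result can be quoted from 259 per arm. That number is 288 less 10% attrition from the sample-size section. It is not a month-4 attack count and is at best an upper bound.

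**Conclusion.** The point holds in this form: the SAP departs from the protocol's conditional definition of recurrence without saying so, and its odds ratio combines the chance of becoming pain-free with the chance of recurrence afterwards. If erenumab raises pain freedom, the bias runs against erenumab. At the assumed 20% versus 30% pain-free with 25% recurrence in both arms, the odds ratio is 1.54 in place of 1.00.

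The size rests wholly on assumed rates. It also assumes that subjects without a qualifying attack are left out. The bias vanishes if pain freedom is equal, and the sign is wrong only when r_E / r_P stays above p_P / p_E. The matter is worth correcting because the month-4 phase is designed to detect the very improvement in triptan response that distorts this endpoint. No primary or secondary conclusion depends on it.

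**What to change.** In SAP 5.1.2, SAP 9.5.3 and Table 9-3 footnote d:
- Restrict recurrence to subjects with NRS = 0 at 2 hours in the first qualifying attack, as in Protocol 11.1. Treat the others as not at risk instead of coding them as no recurrence.
- Use the same 2-hour condition in the numerator, so that the 30- and 60-minute alternatives do not leave numerator and denominator mismatched.
- Apply both changes to the overuse-stratified table.
- Report n/N with a 95% CI by arm and interpret it descriptively, because the pain-free subset forms after randomisation.
- Present it beside 24-hour sustained pain freedom, which is already planned and counts subjects who were not pain-free as failures. That endpoint does not condition on pain freedom, but it still depends on a week 12 dose and a qualifying attack, so it is not a fully randomised comparison either.

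The same edit could state how a pain-free subject with a missing 24-hour value is coded, since non-responder has no clear meaning for an unfavourable event. That is a separate gap.

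The cost is SAP wording and a changed event condition and denominator in the program, with no new data. The downside is a smaller N for one exploratory endpoint.
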